10.2. Analysis of endpoints, individual questions, and assessments

All collected data including withdrawals will be accounted for in listings. All endpoints and baseline information will be listed and summarized by descriptive statistics. The summaries will be done in total and by the different population groups. Summaries and listing will include both safety/ITT and FAS population.

Summary statistics for continuous variables are presented with N, Mean, SD (standard deviation), Median, Min and Max, where N denotes the number of subjects contributing with non-missing data. For discrete variables, summary statistics are presented with N and percentage, where percentage is based on the total number of subjects/observations with non-missing data.

Other summaries and analyses can be made, if relevant.

10.3. Analysis of primary endpoint

The primary endpoint proportion of wounds healed will be analyzed using a binomial proportion test.

The purpose of the primary analysis is to show non-inferiority to the performance of the similar product Aquacel Ag (a silver containing gelling fiber) on proportion of wounds healed, 77 %, with a non-inferiority margin of 20 %. (1)

Since the performance of Aquacel Ag is a fixed proportion, this is equivalent to testing whether the performance of Biatain Fiber Ag is superior to $77 - 20 = 57$ %.

Let the null hypothesis and the alternative hypothesis be defined as:

- $H_0: \mu_{\text{Biatain Fiber Ag}} \leq 57$ % wounds healed
- $H_1: \mu_{\text{Biatain Fiber Ag}} > 57$ % wounds healed

Where Non-inferiority will be demonstrated if H_0 is rejected.

This will be done using the proc freq procedure with a binomial test and if the lower limit of the 95 % confidence interval is above 57 % H_0 is rejected, and the success criteria fulfilled.

Furthermore, as a conservative estimate, a sensitivity analysis will be performed on the primary endpoint, where patients lost to follow-up, or otherwise missing information, will be considered not healed in regards to their wound.

The exploratory endpoints will be analysed descriptively and presented with confidence intervals.

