7.4. Wound healed

If the wound is evaluated by PI or delegate to be healed before or at the termination visit 3 the subject must be terminated according to the termination Wound healed and not according to termination visit 3 as these assessments are not relevant when the wound has healed.

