10.4. Sample size

The primary endpoint is proportion of wounds healed and the sample size calculation is based on a proportion of 77 %. The design is a non-inferiority design, where we want to show noninferiority with a margin of 20 %.

This gives

The POWER Procedure
Z Noninferiority Test for Binomial Proportion

Fixed Scenario Elements	
Method	Normal approximation
Number of Sides	U
Null Proportion	0.77
Margin	-0.2
Alpha	0.025
Binomial Proportion	0.77
Nominal Power	0.8
Variance Estimate	Null Variance

Computed N Total	
Actual Power	N Total
0.801	44

Meaning a total of 44 completers gives a sufficient (80%) power. Accounting for dropouts (10%) gives us 50 subjects.

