10.5. Level of significance and power

The study is designed with a power of 80 % and testing of the primary analysis will be done using a one-sided 0.025 significance level. No other statistical test as pre-planned.

11. Data management

Data management and the final statistical analyses of all measurements described in this protocol are carried out by Clinical Strategies, Coloplast A/S.

Data will be collected through an electronic data capturing (EDC) system on electronic Case Report Form (eCRF), a secure, internet-based case report form. This system will be used to record all subject information collected in the investigation for secure data tracking and centralised data monitoring ("remote monitoring") done by monitors, as defined in the monitoring section.

The system is designed to be compliant with the FDA requirements of 21 CFR part 11. It is a validated data management system allowing only qualified and trained personnel to enter the system. The system has full audit trail and electronic signature.

The data management system has restricted role-based access control. The principal investigator or delegate must be trained in the system prior to getting access. The sponsor will be responsible for training the investigator or delegate, in completion of the eCRF. The training is web-based and must be completed before access to the investigation is granted. Training will be documented in the data management system. The data manager will also demonstrate the system on a virtual meeting. Only the principal investigator, or delegate, will be authorised to enter data in the eCRF.

The monitor, using his/her personal login information shall verify all critical data points against the source documents and issue electronic queries for the authorised clinical site personnel to respond, as defined in the monitoring section.

A critical quality control will be performed by the sponsor's data management team and queries issued where needed. Such queries must be resolved by the site personnel.

The principal investigator, using his/her personal login information, shall sign each eCRF.

Automated, real-time access to the data enable control on study compliance and safety assessments.

A full audit trail ensures, that each user's (site personnel, monitor, sponsor, data manager) access to and actions in the system is tracked.

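### If subjects with no day-14 status are dropped, as 10.2 to 10.4 imply but never state, losses after V2 remove only wounds still unhealed and push the healed percentage upward, even when dropout is unrelated to healing

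*Combined protocol and SAP*

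**What the plan says.** - **Primary test (10.3, 10.5).** The healed proportion is compared with 57%, which comes from "77 %, with a non-inferiority margin of 20" per cent. Success needs the lower 95% limit above 57%, and "testing of the primary analysis will be done using a one-sided 0.025 significance level".
- **Missing outcomes (10.3).** The only rule given belongs to a secondary analysis: "a sensitivity analysis will be performed on the primary endpoint, where patients lost to follow-up, or otherwise missing information, will be considered not healed". Success is not tied to that analysis.
- **Denominator (10.2, 10.4).** For discrete variables, "percentage is based on the total number of subjects/observations with non-missing data". The sample size is counted in completers: "Meaning a total of 44 completers gives a sufficient (80%) power", raised to 50 enrolled for 10% dropout.
- **When a success is fixed (7.4).** If the wound is judged "healed before or at the termination visit 3 the subject must be terminated according to the termination Wound healed". This subject has no V3.
- **When a failure is fixed (5.4, 7.1, 7.3).** Healing is recorded yes/no at V2, but the endpoint is healing within 14 (+/- 2) days. A 'No' at day 7 leaves it open until V3. No study wound assessment is made at unscheduled visits.
- **Withdrawals (5.1, 6.4).** Withdrawn subjects are encouraged to attend V3 and are not replaced.

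**The concern.** The two outcomes become known at different times. A subject healed at V2 has a final success and cannot go missing afterwards. A subject unhealed at V2 has no final outcome unless seen again. If the primary proportion uses only subjects with a known outcome, everyone lost after V2 comes from the unhealed group, and those who remain are enriched for early healers. The percentage then no longer estimates the proportion healed by day 14, even if dropout has nothing to do with healing.

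This matters because the trial has one arm and one test against a fixed 57%, so no control group shares the distortion. The planned alternative, missing counted as not healed, errs the other way. Under random dropout the two analyses bracket the day-14 rate, but neither estimates it, and the plan has no rule for the case where they disagree.

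**Working it through.** **The plan's own figure.** Inputs from 10.3 to 10.5: null 0.57, assumed proportion 0.77 ("the sample size calculation is based on a proportion of 77" per cent), one-sided 0.025, power 80%.

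n = [(1.960 × √(0.57 × 0.43) + 0.842 × √(0.77 × 0.23)) / 0.20]² = 43.86, so 44, with power 0.801. This reproduces the plan. 44/0.9 = 48.9, so 49 against the stated 50, which is close enough.

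**Model for the bias.** Let p be the true proportion healed by day 14, h the proportion of all wounds healed at V2, and d the chance that a subject unhealed at V2 is lost before V3, independent of healing. Neither h nor the timing of dropout is in the documents. I take h = 20 to 40% as an assumption and 10% missing overall from 10.4. Then

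completer proportion = [h + (p − h)(1 − d)] / [h + (1 − h)(1 − d)],

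which exceeds p whenever h > 0, d > 0 and p < 1.

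**All dropout after V2**, d = 0.10/(1 − h), p = 0.57:

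- h = 0.20, d = 0.125: (0.20 + 0.37 × 0.875)/0.90 = 0.5237/0.90 = 0.582
- h = 0.30, d = 0.143: (0.30 + 0.27 × 0.857)/0.90 = 0.5314/0.90 = 0.590
- h = 0.40, d = 0.167: (0.40 + 0.17 × 0.833)/0.90 = 0.5417/0.90 = 0.602

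The numerators are what missing = not healed would estimate: 52.4%, 53.1% and 54.2%, all below the true 57%.

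**Dropout spread over both weeks**, with the same d each week and d + (1 − d)(1 − h)d = 0.10, so d = 0.057, 0.060 and 0.064. Week-1 losses before healing is scored cancel from the ratio. The formula gives 0.5751, 0.5781 and 0.5815.

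**False success at a true 57%** (50 enrolled, 10% missing):

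| Scenario | Bias, points | Score limit | Exact limit |
|---|---|---|---|
| No wound healed before V3 | 0 | about 2.3% | 1.8% |
| Spread over both weeks, h = 20 to 40% | 0.5 to 1.2 | 2.7 to 3.4% | 2.1 to 2.6% |
| All after V2, h = 20 / 30 / 40% | 1.2 / 2.0 / 3.2 | 3.3 / 4.3 / 5.9% | 2.6 / 3.4 / 4.8% |
| All before any healing is recorded | 0 | about 2.3% | 1.8% |

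At a true 77% with all dropout after V2, the completer proportion averages 77.6%, 78.1% and 78.7%.

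**A worked case (hypothetical).** Fifty are treated, 20 are healed at V2, 5 of the 30 unhealed are then lost, and 13 of the remaining 25 heal.

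- Completers: 33/45 = 73.3%, lower limit 59.0% (score) or 58.1% (exact). Success.
- Product-limit: unhealed = 30/50 × 12/25 = 0.288, so healed 71.2%. Greenwood variance = 0.288² × [20/(50 × 30) + 13/(25 × 12)] = 0.0047. Effective n = 0.712 × 0.288/0.0047 = 43.6. Lower limit 56.5% (score) or 55.5% (exact). No success.
- Missing = not healed: 33/50 = 66.0%, lower limit 52.2% (score) or 51.2% (exact). No success.

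With Wald limits the first two both pass (60.4% and 57.8%), so the conflict between them depends on the type of interval.

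**The case against.** **The rule is inferred.** Section 10.3 never says that subjects without V3 are removed. The non-missing sentence in 10.2 describes summary statistics, and the full analysis set in 10.1 needs only some endpoint information. A V2 'No' followed by loss could be read as not healed, and then there would be no inflation. This stands as a limit on the claim. However, naming lost = not healed as a separate sensitivity analysis makes little sense if the primary analysis already does it, so the completer reading is the more natural one. On either reading the rule has to be written down.

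**Early V3 visits work the other way.** A withdrawn subject who attends an early V3 scored 'No' enters as a failure, which offsets some of the bias. This also stands. It does not help for subjects who cannot be reached, and the plan itself budgets 10% dropout.

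**The large figures need strong assumptions.** The highest need all dropout after V2 and 40% of wounds healed by about day 7. With spread dropout and an exact limit, false success is essentially nominal. That is correct.

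**The sensitivity analysis would flag a fragile result.** In the worked case it does. But it is biased low under random dropout and has no role in the success rule, so it shows a conflict without settling it.

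**A simple two-visit life table is not enough.** Under 7.4, second-week healers leave by the healed-wound termination and not V3, so a formula built on V3 attendance would miss them. Subjects lost before V2 also need a place in the first interval. Even with these repairs, if second-week healing is recorded before V3, the two-interval estimate still averages about 58.2 to 58.4% at a true 57% in simulation. The fix below is worded for this.

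**Conclusion.** The concern holds in a limited form. The primary missing-data rule is unstated. Under the reading that 10.2 to 10.4 imply, dropout after V2 that is unrelated to healing can only raise the healed percentage. With 10% dropout and an assumed 20 to 40% healed at V2, the rise runs from about 0.5 to 3.2 points according to when dropout occurs. It is zero if no wound heals before V3, or if all loss comes before any healing is recorded.

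A reader might infer more, in three ways that the documents do not support:

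- That the plan instructs exclusion of subjects without V3. It implies this but does not say it.
- That the one-sided 0.025 level is definitely broken. That depends on the share healed at V2, the timing of dropout and the type of interval, none of which the plan fixes. A Wald limit exceeds 0.025 even with no early healing (3.3%), which is a separate matter.
- That the bias always favours success. This holds only for dropout unrelated to healing. If, for example, subjects stay away because they have healed, the direction can reverse.

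**What to change.** In 10.3:

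1. State how the primary analysis treats a subject with a V2 'No' and no later assessment, and a subject lost before V2.
2. Estimate the day-14 cumulative healed proportion over all treated subjects with a product-limit estimate, interval-censored where needed. Count healing recorded at V2, at any healed-wound termination visit or at V3, by its actual date. Censor subjects without a day-14 status at their last recorded unhealed assessment, including those lost before V2.
3. Compare its lower 95% limit with 57%, either as the primary analysis or, at minimum, as a prespecified sensitivity analysis beside the completer proportion.
4. Keep missing = not healed as the conservative sensitivity analysis, and report the number without a day-14 status by last recorded status.

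The cost is a few sentences and a little code, using healed yes/no entries and visit dates already collected. The reported rate will be slightly lower when there is dropout. Some upward bias remains if second-week healing dates are recorded but last unhealed assessments are not. Simulated power of the product-limit analysis at 77% healing and 10% dropout is 0.79 to 0.81, in line with 10.5 ("The study is designed with a power of 80" per cent).

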10.4. Sample size

The primary endpoint is proportion of wounds healed and the sample size calculation is based on a proportion of 77 %. The design is a non-inferiority design, where we want to show noninferiority with a margin of 20 %.

This gives

The POWER Procedure
Z Noninferiority Test for Binomial Proportion

Fixed Scenario Elements	
Method	Normal approximation
Number of Sides	U
Null Proportion	0.77
Margin	-0.2
Alpha	0.025
Binomial Proportion	0.77
Nominal Power	0.8
Variance Estimate	Null Variance

Computed N Total	
Actual Power	N Total
0.801	44

Meaning a total of 44 completers gives a sufficient (80%) power. Accounting for dropouts (10%) gives us 50 subjects.

10.5. Level of significance and power

The study is designed with a power of 80 % and testing of the primary analysis will be done using a one-sided 0.025 significance level. No other statistical test as pre-planned.

11. Data management

Data management and the final statistical analyses of all measurements described in this protocol are carried out by Clinical Strategies, Coloplast A/S.

Data will be collected through an electronic data capturing (EDC) system on electronic Case Report Form (eCRF), a secure, internet-based case report form. This system will be used to record all subject information collected in the investigation for secure data tracking and centralised data monitoring ("remote monitoring") done by monitors, as defined in the monitoring section.

The system is designed to be compliant with the FDA requirements of 21 CFR part 11. It is a validated data management system allowing only qualified and trained personnel to enter the system. The system has full audit trail and electronic signature.

The data management system has restricted role-based access control. The principal investigator or delegate must be trained in the system prior to getting access. The sponsor will be responsible for training the investigator or delegate, in completion of the eCRF. The training is web-based and must be completed before access to the investigation is granted. Training will be documented in the data management system. The data manager will also demonstrate the system on a virtual meeting. Only the principal investigator, or delegate, will be authorised to enter data in the eCRF.

The monitor, using his/her personal login information shall verify all critical data points against the source documents and issue electronic queries for the authorised clinical site personnel to respond, as defined in the monitoring section.

A critical quality control will be performed by the sponsor's data management team and queries issued where needed. Such queries must be resolved by the site personnel.

The principal investigator, using his/her personal login information, shall sign each eCRF.

Automated, real-time access to the data enable control on study compliance and safety assessments.

A full audit trail ensures, that each user's (site personnel, monitor, sponsor, data manager) access to and actions in the system is tracked.

The Data Validation Plan describes which edit checks, range checks, and other consistency checks that will be done on the clinical data during conduct of the investigation. The Data Validation Plan will be developed in collaboration with the Clinical Manager and the Statistician and will be aligned with the monitoring section.

Principal Investigator, or delegate, at the clinical site will perform primary data collection directly into the eCRF or drawn from source-document (i.e., medical records) reviews. The eCRF will be completed on a continuous basis starting from the point of enrolling the subject to final follow up.

The eCRF will be completed by the investigator, or delegate, who have signed the Site Personnel Signature and Delegation List and Clinical Investigation Training Log. It will be the responsibility of the investigator to ensure that all measurements and observations are correctly noted in the eCRF.

All assessments and observations throughout the investigation for each subject must be carefully recorded in an eCRF during the visit or immediately after. The eCRF makes it possible to enter data right away when they are obtained. This is the preferred way of collecting data. In case this is not possible the data should be entered no later than 7 days after the visit / procedure.

In the unforeseen situation, where site cannot establish connection to the EDC system, a paper CRF (pCRF) has been printed and supplied by sponsor.

The wound area is measured by an [REDACTED] delivered by [REDACTED] The PI, or delegate, will download an app to a Smartphone. The app can be used to take a photo of the wound. The photo is then uploaded to [REDACTED] Imaging platform where a designated person will perform the area measurement. The results will afterwards be entered into [REDACTED]

At the end of the study a formal data review meeting will be performed before the database will be locked.

The Data Management Procedures are further described in the Data Management SOPs.

The investigator will keep a separate list of the subjects' ID numbers, names, and addresses in a locked room/cabinet. Only data referred to in this clinical investigation plan will be recorded in the CRFs.

Adverse events should be registered following the timelines described in the Adverse Event section.

11.1. Remote monitoring

Remote or centralized monitoring is a remote evaluation carried out by sponsor personnel or representatives (e.g., data management personnel, statisticians, or clinical monitors) at a location other than the site(s) at which the clinical investigation is being conducted. Remote monitoring processes can provide many of the capabilities of on-site monitoring as well as additional capabilities.

In addition to onsite monitoring visits, remote monitoring of the data entered in the e-CRF system could be used to achieve the following:

- Conduct activities such as: standard checks of range, consistency, and completeness of data and checks for unusual distribution of data, such as too little variance)
- Special attention will be given in case of frequent data anomalies or errors, protocol violations or excessive dropouts.
- Augment on-site monitoring by performing monitoring activities that can only be accomplished using centralized processes (e.g., statistical analyses to identify data trends not easily detected by on-site monitoring)
- Monitor data quality through routine review of submitted data in real-time to identify missing data, inconsistent data, data outliers, and potential protocol deviations that may be indicative of systemic and/or significant errors in data collection and reporting at the site
- Verify source data remotely, provided that both source data and CRFs can be accessed remotely
- Conduct aggregate statistical analyses of study data to identify subject data that are outliers relative to others and to evaluate individual subject data for plausibility and completeness
- Conduct analyses of site characteristics, performance metrics (e.g., high screen failure rates, high frequency of eligibility violations, and delays in reporting data), and clinical data to identify early on corrective actions needed for characteristics correlated with poor performance or noncompliance.

11.2. Data retention

The PI file must be archived for a minimum period of 10 years after the final clinical investigation report has been signed.

12. Amendments to the Clinical Investigation Plan

No changes in the clinical investigation procedures shall be affected without mutual agreement between the PI and the sponsor. The agreement of the changes must be documented by signing the corresponding clinical investigation plan amendments and registered in the Change Log.

All significant changes require notification to the EC and applicable regulatory authority. Substantial changes may require approval from the EC and applicable regulatory authority prior to implementation. (Example of significant change: Changes of inclusion criteria, end points or assessment methods)

13. Deviations from the Clinical Investigation Plan

Deviations to the Clinical Investigation Plan occurs when the activities during the clinical investigation do not comply with the EC/CA approved investigation plan. Minor deviations are defined as those that don't increased risk, decrease benefit, or don't have a significant effect on the subject's rights, safety or welfare; and/or on the integrity of the data. If a deviation increases risk or decreases benefit and/or has a significant effect on the subject's rights, safety, or welfare and/or has a significant effect on the integrity of the data it is defined as a major deviation and the Investigator must inform the monitor immediately, and the monitor will report and inform the Clinical Manager or designee immediately.

The investigator is not allowed to deviate from the Clinical Investigation Plan unless, under emergency circumstances or to protect the rights, safety, and welfare of the subject(s).

For the purposes of this investigation, any variance from the protocol is considered a deviation and is to be reported.

The site will complete a deviation eCRF for all data-related deviations and all deviations that are not related to the data (for example, an untrained nurse performing study procedures) are reported by the monitor in the Site Report – Periodic Monitoring and actions are addressed to the Investigator for completion.

If any deviations to the investigation plan are detected during the monitoring visit, the Monitor shall ensure the site reports all deviations in the eCRF or on the Deviation log in the Investigator File. Additionally, the monitor must report any deviation noted during the visit in the Periodic Monitoring Report.

Monitor will align with data management in each investigation, how data management will be informed about all deviations.

The following information about the deviation will be collected:

- Site ID, Subject ID
- Date the deviation took place.
- State what the deviation is related to.
- Does the deviation affect data integrity?
- Does the deviation affect the subject's safety?
- Clear and concise description of the event.
- Corrective action taken.

14. Device Accountability

All access to the investigational devices used in the clinical investigation is controlled by storage procedures and device accountability logs as described below. The investigational devices must only be used in this clinical investigation and only according to the CIP.

Sponsor keeps a device accountability log that states the physical location of all investigational devices from shipment of investigations devices to the investigational sites until return of or disposal.

The PI or delegate, keeps records documenting the receipt, use and return and disposal of the investigational devices, which includes:

- Name of product received
- Date of receipt.
- Identification of each investigational device (batch no./serial no./unique code).
- The expire date (if applicable)
- Number of products received
- The date(s) of use.
- Number of products distributed to subjects
- Subject identification.
- The date on which the investigational device was returned/explanted from the subject, if applicable.
- The date of return unused, expired or malfunctioning investigational devices, if applicable.

15. Statement of compliance

The clinical investigation is conducted in accordance with:

- Ethical principles that have their origin in the Declaration of Helsinki, 1964, Last amended at the 59th WMA General Assembly, Brazil, October 2013.
- MDR (EU) 2017/745
- ISO 14155:2020 “Clinical Investigation of medical devices for human subjects – Good clinical practices”.
- Any applicable regional or national regulations will be specified in the country specific CIP.

